5.3 Screen Failures

A screen failure occurs when a participant who has consented to participate in the clinical study is not subsequently randomized to study drug. A minimal set of screen failure information will be collected in the electronic data capture (EDC) system and will include date of informed consent, demography (as allowed by local law), failed eligibility criteria, and SAEs.

Individuals who fail screening may be rescreened after discussion with Sponsor's Medical Monitor. Participants should be assigned a new participant number for every screening/rescreening event.

6 STUDY DRUGS AND CONCOMITANT THERAPY

Study drugs are all pre-specified, investigational products intended to be administered to the study participants during the study conduct.

6.1 Study Drugs Administered

Study drugs include WVE-006 and placebo. Details on study drugs are provided in [Table 9](#).

Table 9 Study Drugs Administered

Study Drug Label	WVE-006	Placebo
Study Drug Name	WVE-006	Placebo
Study Drug Description	Period 1: SC injection, one dose per participant at varying dose levels. Period 2: SC injection, Q2W at a dose level identified in Period 1.	Period 1: SC injection, once per participant. Period 2: SC injection, Q2W.
Type	Drug	Drug
Dose Formulation	Lyophilized powder for reconstitution	0.9% normal saline, sterile solution for injection
Unit Dose Strengths	CCI per vial	N/A
Dosage Levels	Period 1: single dose Starting Dose: 30 mg Highest dose: see Section 4.1.2 Period 2: Q2W dosing for a total of 3 doses at the dose level selected from Period 1	N/A (same volume as corresponding WVE-006 dose)
Route of Administration	SC injection	SC injection
Use	Experimental	Placebo
Sourcing	Provided centrally by the Sponsor	Provided locally by the site
Packaging and Labeling	Study drug will be provided in 10 mL single use vial. Each vial will be labeled as required per country requirement.	N/A

Abbreviations: SC = subcutaneous; Q2W = every other week

Table 10 Study Periods

Period Title	Period 1	Period 2
Period Type	Single ascending dose	Multiple dose
Period Description	Participants will receive WVE-006 or placebo once SC starting at 30 mg and escalating as per the study schema.	Participants will receive a total of 3 doses of WVE-006 or placebo Q2W SC at the MTD, highest dose, or other selected dose

	Participants will be followed for 12 weeks.	from Period 1. Participants will be followed for 12 weeks following last study drug administration.
Associated Study Drug Labels	WVE-006, Placebo	WVE-006, Placebo

6.2 Preparation, Handling, Storage, and Accountability

1. The Investigator or designee (e.g., pharmacy staff) must confirm appropriate conditions (e.g., temperature) have been maintained during transit for all study drug received, and any discrepancies are to be reported and resolved before use of the study drug.
2. Only participants enrolled in the study may receive study drug, and only authorized site staff may supply, prepare, or administer study drug.
3. WVE-006 must be stored in a secure, environmentally controlled, and monitored (manual or automated) area in accordance with the labeled storage conditions with access limited to the authorized pharmacy staff.
4. The designated staff is responsible for study drug accountability, reconciliation, and record maintenance (i.e., receipt, reconciliation, and final disposition records).
5. The Investigator, pharmacy, and site staff must ensure that study blind is maintained; see [Section 6.5](#) for more information.
6. Returned study drug should not be re-dispensed to participants.
7. Further guidance and instructions for the preparation, handling, storage, accountability, and disposition of study drug is provided in the Pharmacy Manual.

6.3 Study Drug Administration

Study drug will be dispensed at the study visits as summarized in the SoA.

Participants are dosed at the site and will receive study drug directly from the Investigator or designee, under medical supervision. Anatomical SC injection sites will be determined by the Investigator for each participant; if the abdomen is selected as an injection site, it is recommended that the participant be supine when the injection is administered. Rotation of injection sites for multiple dose period is allowed per the Investigator's judgment. The date, time, and anatomic location of each dose administered in the clinic will be recorded in the source documents and eCRF. The dose of study drug and study participant identification will be confirmed at the time of dosing by a member of the study site staff other than the person administering the study drug. Please refer to the Study Manual for additional details regarding administration of study drug.

6.4 Assignment to Study Drug

All participants will be assigned to randomized study drug per assigned randomization schedule. Details will be provided in the randomization plan and executed per site standard.

6.5 Blinding

In order to maintain the blinding of the study drug (WVE-006 or placebo), all study personnel will be blinded to participant treatment assignment. Physicians, nurses, participants, contract research organization (CRO) staff, and any study personnel performing participant assessments must NOT be informed of the participant's treatment assignment (see Study Manual) except if unblinding is required or as required by regulatory authorities ([Section 6.5.1](#)).

The pharmacy personnel will be unblinded to prepare doses of study drug to ensure that the clinical site staff responsible for administering study drug and conducting assessments per the protocol, and the participant remain blinded to study treatment. In addition, a clinical research associate will be unblinded to perform drug accountability.

6.5.1 *Breaking the Blind*

6.5.1.1 *Unblinding In Case Knowledge of Treatment May Impact Medical Management*

To maintain the overall quality of data collected during the study, breaks in blinding during the conduct of the study should occur only in exceptional circumstances when knowledge of the actual treatment is essential for further management of the participant. Unblinding of the study drug for an individual can be done during the study period in the case of:

- Any AE where knowledge of the treatment assignment is deemed necessary to treat the participant
- Pregnancy of a participant or participant's partner in the study

Procedures for unblinding will be described in a Study Manual supplied to the site. The investigator should make every effort to contact the Sponsor's Medical Monitor before unblinding a participant's treatment assignment unless this could delay emergency treatment of the participant. In all circumstances other than a medical emergency, unblinding will be done only after discussion with the Sponsor's Medical Monitor. Emergency treatment unblinding must be reported to the Sponsor's Medical Monitor immediately. When it is necessary to break the blind, the investigator must notify the Ethics Committee (EC)/Institutional Review Board (IRB) as applicable. If a participant is unblinded, the participant will discontinue further treatment with study drug (i.e., MD) and will have either a routine scheduled visit if due or an unscheduled visit as soon as possible to evaluate the safety concern that prompted the unblinding.

If unblinding is deemed necessary, the Investigator should not disclose the treatment assignment to other study personnel until after database lock.

6.5.1.2 *Recording the Unblinding*

If an unblinding occurs, the following information should be captured at a minimum:

- Participant information
- Reason for unblinding
- Date and time of unblinding
- Name of the person requesting/responsible for unblinding.

How unblinding should be reported to the Sponsor will be detailed in a Study Manual.

6.6 Study Drug Compliance

The date, time, and anatomic location of each dose administered in the clinic will be recorded in the source documents. Errors in administration (e.g., incorrect dose, injection to incorrect anatomic area) or unexpected issues with injection should be documented and reported to the Sponsor's Medical Monitor.

6.7 Dose Modification

Dose modifications are not applicable in Period 1 since only a single dose will be administered per participant.

Participants in Period 2 will receive the DMC-approved dose at the time of their enrollment. If the DMC determines that a dose reduction is needed AFTER treatment in Period 2 has started, participants who have started study treatment in Period 2 will receive their remaining doses at the reduced dose level.

For dose modifications due to TEAEs, refer to [Section 7.1.2](#).

6.8 Continued Access to Study Drug after the End of the Study

Continued access to WVE-006 is not planned following the end of study.

6.9 Treatment of Overdose

The study drugs are planned to be administered by trained study staff. Administration will be performed in accordance with this protocol and instructions in a Study Manual. Any incidence of overdose should be recorded as a deviation.

No data are available regarding overdose with WVE-006. As with any agent, if overdose occurs, general supportive measures and close observation should be instituted. Misuse of the study drug is not expected in this study as participants have no direct access to the study drug.

6.10 Prior and Concomitant Therapy

Medications with a start date before the first dose of investigational drug will be classified as prior medications. Any medication that the participant began taking after the first dose of investigational drug will be classified as concomitant. Any medication that a participant started before the first dose of investigational drug and continued to take during the study will be classified as both prior and concomitant. Any medication that was stopped on the same day as the first dose of investigational drug will be considered a prior medication. If the stop date of a given medication is missing, then the medication will be classified as concomitant.

It is required that the drug name, dose, indication, and the dates of administration are to be recorded. This will include all prescription drugs, herbal products, vitamins, minerals, and over-the-counter medications. Any changes in concomitant medications will also be recorded in the participant's electronic case report form (eCRF).

Any concomitant medication deemed necessary for the welfare of the participant during the study may be given at the discretion of the Investigator. However, prophylactic medications for injection site reactions are NOT permitted unless first discussed between the Investigator and Medical Monitor.

Prescription or non-prescription drugs, including vitamins, herbal and dietary supplements should not be taken throughout the duration of the study unless required to treat an AE, with the exception of paracetamol and ibuprofen.

Participants should not receive a vaccination, including COVID-19 vaccine injection, within 14 days prior to first dose until completion of the post-study follow up visit.

If intake of any prior or concomitant medication is necessary during the study, the daily dosage, duration and reasons for administration will be recorded on the participant's eCRF.

7 DISCONTINUATION OF STUDY DRUG AND PARTICIPANT DISCONTINUATION/WITHDRAWAL

Participants are free to withdraw from the study or discontinue study treatment at any time upon request without prejudice to their future medical care by the Investigator or at the study site. Participation in the study may also be stopped at any time at the discretion of the Investigator or at the request of the Sponsor. Participants who withdraw or discontinue from study treatment will no longer receive investigational drug.

7.1 Discontinuation of Study Treatment in Period 2

A participant must permanently discontinue study treatment for any of the following:

- The participant is withdrawn from the study ([Section 7.1.2](#)).
- The participant experiences an AE that in the Investigator's opinion requires treatment discontinuation.
- A change in the participant's medical condition not consistent with the protocol requirements or that justifies discontinuation of study drug.
- Pregnancy (refer to [Section 10.3.6](#)).

If a participant discontinues treatment, they will be encouraged to complete the ET visit, unless consent is withdrawn.

The reason for discontinuation of study treatment must be recorded in the eCRF and source documentation.

7.1.1 *Period 2 Individual Stopping Criteria:*

Dosing will be paused or discontinued (per Investigator judgment) for an individual participant at any time in the study if:

- Participant experiences any severe event or SAE considered at least possibly related to study drug.
- Participant experiences clinically significant hypersensitivity to WVE-006 (or placebo) administration.
- Participant has any medical condition that is judged by the Investigator to jeopardize the participant's safety if he or she continues to receive the study drug.

7.1.2 *Withdrawal of Participants from the Study*

Participants must be withdrawn from the study for any of the following:

- The participant withdraws consent
 - At the discretion of the Investigator for medical reasons
-

- At the discretion of the Investigator or Sponsor for noncompliance
- Major protocol deviation that may impact interpretation of data (after discussion with Sponsor) (see [Section 10.5.2](#))
- Termination of the study by the Sponsor (see [Section 10.1.9](#))
- At the discretion of the Sponsor for any reason

Any participant for whom consent to participate in the study is withdrawn will be removed from further treatment and study observation immediately upon the date of request. If possible, the early termination study procedures ([Section 4.1.4](#)) and observations should be completed before the participant withdraws consent. All information, including the reason for withdrawal from the study (if known), must be recorded in the eCRF and source documentation. Any information collected prior to withdrawal of consent will be used for study purposes.

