Dose escalation will be paused until further evaluation by the DMC if any of the following criteria are met. If it is confirmed that a stopping criterion was met, no further dosing will take place until after submission and approval of a substantial amendment if the DMC recommends the trial can continue.

- One or more participants experiencing at least possibly related Common Terminology Criteria for Adverse Events (CTCAE) Grade ≥ 3 TEAE or CTCAE grade ≥ 3 laboratory abnormality in a single cohort.
 - All grade 3 toxicities for vital signs must be confirmed with a repeat measurement obtained within 1 hour.
 - All grade 3 toxicities for laboratory parameters must be confirmed with a repeat measurement obtained within 24 hours.
- Two or more participants experiencing at least possibly related CTCAE grade ≥ 2 TEAEs or CTCAE Grade ≥ 2 laboratory abnormalities in a single cohort.
 - All grade 2 toxicities for vital signs must be confirmed with a repeat measurement obtained within 1 hour.
 - All grade 2 toxicities for laboratory parameters must be confirmed with a repeat measurement obtained within 24 hours.
- One or more participants experiencing any at least possibly related SAE in a single cohort.

Period 2 Individual Stopping Criteria:

Dosing will be paused or discontinued (per Investigator judgment) for an individual participant at any time in the study if:

- Participant experiences any severe or serious adverse event considered at least possibly related to study drug.
- Participant experiences, in the Investigator's opinion, clinically significant hypersensitivity to WVE-006 (or placebo) administration.
- Participant has any medical condition that is judged by the Investigator to jeopardize the participant's safety if he or she continues to receive the study drug.

On discontinuation of treatment, participants will be encouraged to continue follow-up for safety per protocol. Per Investigator judgment with consultation with the Sponsor, the participant may be allowed to resume participation in the study if/when the event has resolved.

Sponsor: Wave Life Sciences UK Limited	Investigational Product: WVE-006	Developmental Phase: Phase 1	IRAS ID Number: 1008635

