7.4 Replacements

In Period 1 or 2, additional participants may be enrolled as replacements for discontinued or withdrawn participants (refer to [Section 7](#)) in consultation with the Sponsor.

Any participants enrolled but withdrawn prior to the first dose will be replaced. Any participants withdrawn or discontinued after receiving at least one dose may be replaced at the discretion of the Sponsor.

Enrollment/randomization numbers will not be reused. A new, unique enrollment/randomization number will be given to the new participant.

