9.2 Analysis Populations

The following analysis sets will be defined for SAD and multiple-dose portions of the data analyses.

- Safety population will include randomized participants who have received at least 1 dose of study medication. The safety population will be the analysis set used for summaries of safety data collected in the respective period.
- PK population will consist of participants in the safety population with at least 1 post dose plasma concentration measurement.

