10.5.2 Protocol Deviations

A deviation from the protocol is any change, divergence, or departure from the study design or procedures defined in the protocol and associated manuals, ICF, recruitment process, or study materials approved by the Sponsor, Investigator, and the IRB/EC.

Important protocol deviations are a subset of protocol deviations that might significantly affect the completeness, accuracy, and/or reliability of the study data or that might significantly affect a participant's rights, safety, or well-being. For example, important protocol deviations might include enrolling participants in violation of key eligibility criteria designed to ensure a specific study population or failing to collect data necessary to interpret primary endpoints, as this may compromise the scientific value of the study.

All processes and procedures defined in this protocol must be adhered to. Emergency departures from the protocol that eliminate an apparent immediate hazard to a particular participant and that are deemed by the Investigator as crucial for the safety and well-being of that participant may be instituted for that participant only and documented as deviations. The Investigator will contact the Medical Monitor as soon as possible regarding such a deviation. These departures do not require preapproval by the IRB/EC; however, the IRB/EC and Medical Monitor must be notified in writing as soon as possible in accordance with the IRB/EC policies after the departure has been made.

Protocol deviations will be documented by the clinical monitor in the clinical study management system and on monitoring reports throughout the course of monitoring visits. Investigators will be notified in writing by the monitor of deviations. As required by local regulatory authorities, the Investigator will notify the IRB/EC of any applicable protocol deviations in a timely manner.

No protocol deviations to eligibility, also known as waivers, will be permitted.

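### Section 7.1.2 can end follow-up of dosed participants because of a protocol deviation or noncompliance, so later non-serious events and laboratory data go uncollected while they stay in the TEAE denominator

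*Combined protocol and SAP*

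**What the plan says.** Section 7.1.2 opens with "Participants must be withdrawn from the study for any of the following". Its list includes "Major protocol deviation that may impact interpretation of data (after discussion with Sponsor" and, separately, "At the discretion of the Investigator or Sponsor for noncompliance". The deviation ground concerns the usefulness of the data, not the safety of the participant. Nothing in the list treats dosed participants differently or distinguishes stopping study drug from ending observation.

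Other sections determine what follows:

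- Section 4.1.4 asks for one ET visit after early withdrawal.
- Section 10.3.2 ends AE collection at the last study visit or the ET visit.
- Section 9.3.5.1 closes the TEAE window when the participant completes or discontinues the study, and bases TEAE percentages on everyone in the dose group.
- Section 9.2: "Safety population will include randomized participants who have received at least 1 dose of study medication".
- Section 7.4: "Any participants withdrawn or discontinued after receiving at least one dose may be replaced at the discretion of the Sponsor".

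Two neighbouring texts do not line up. On stopping treatment, the synopsis says "On discontinuation of treatment, participants will be encouraged to continue follow-up for safety per protocol", whereas Section 7.1 encourages only the ET visit. Section 7.1.2 refers to Section 10.5.2 for its *major* deviations, but that section defines a different term: "Important protocol deviations are a subset of protocol deviations that might significantly affect the completeness, accuracy".

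**The concern.** The primary objective is safety, and the first endpoint is TEAE incidence. A withdrawal rule based on data interpretability can shorten the observation of that endpoint in someone already exposed. The participant still counts in the denominator, while non-serious events starting after the ET visit, and later laboratory results, are not sought. Any error this causes in crude incidence is downward.

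Period 1 is the clearest case. After the single dose on Day 1 there is no treatment left to stop, so withdrawal removes only observation. The dose groups are small, with up to 6 active participants per cohort, so one truncated record is a visible share of what is known about a dose. The Period 2 dose decision also draws on at least 4 weeks of Period 1 safety data at the proposed dose (Section 4.1.2).

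**Working it through.** **Inputs.** Cohort of up to 6 active and up to 2 placebo (synopsis). Period 1: dose on Day 1, follow-up to Day 85, visits on Days 8, 15, 22, 29, 36, 43, 50, 57, 64, 71, 78 and 85 (Table 1, Section 8.5), which is 12 visits. Period 2: follow-up to Day 113 (synopsis). The plan gives no withdrawal, deviation or event rate, so it has no figure of its own to reproduce here. Its planned enrolment is consistent with the cohort sizes: 5 × 8 + 8 = 48, and 48 + 8 = 56 with the optional cohort.

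**Step 1: scheduled follow-up lost.** Period 1 has 85 − 1 = 84 post-dose days. Leaving on Day d loses 85 − d of them, plus every scheduled visit after Day d. The ET visit is set aside.

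| Leaves Period 1 on | Days lost of 84 | Visits lost of 12 |
|---|---|---|
| Day 8 | 77 (92%) | 11 |
| Day 15 | 70 (83%) | 10 |
| Day 29 | 56 (67%) | 8 |
| Day 57 | 28 (33%) | 4 |

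Period 2 has 113 − 1 = 112 days from first dose. Leaving on Day 15 loses 98 (88%), and leaving on Day 29 loses 84 (75%).

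**Step 2: possible effect on crude incidence (assumed values).** Let each of 6 active participants have the same TEAE risk p. One is withdrawn, with a fraction f of that person's risk falling after observation ends. The denominator stays 6, as Sections 9.2 and 9.3.5.1 require. Expected crude incidence relative to the truth is

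[5p + p(1 − f)] / 6p = 1 − f/6.

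This gives 100% at f = 0, 92% at f = 0.5 and 83% at f = 1.

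The chance of recording at least one event is 1 − (1 − p)^6 with full follow-up and 1 − (1 − p)^5 × [1 − p(1 − f)] with one truncated record:

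| Assumed p | Full follow-up | f = 0.5 | f = 1 |
|---|---|---|---|
| 5% | 26.5% | 24.6% | 22.6% |
| 10% | 46.9% | 43.9% | 41.0% |
| 20% | 73.8% | 70.5% | 67.2% |
| 30% | 88.2% | 85.7% | 83.2% |

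The column f = 1 is an outer bound. It supposes that nothing of the withdrawn participant's risk was observed, which cannot be quite true after the 48-hour in-clinic stay in Period 1. If events cluster in the first days and withdrawal comes late, f is near 0 and so is the effect.

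**The case against.** Much can be said for the plan, and most of it stands as a limit on the point.

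- **The rule is less automatic than its opening line.** Noncompliance is at the discretion of the investigator or sponsor, and the deviation ground follows discussion with the sponsor. A reader might infer that both force removal; the noncompliance item does not.
- **Data are not thrown away.** A reader might infer that the withdrawn participant's record is discarded. Section 9.2 keeps every dosed participant, and the Period 1 ET visit repeats laboratory tests, PK, immunogenicity sampling, physical examination, vital signs, ECG and AE review (Table 1). Known SAEs are followed until resolved or stable (Section 10.3.5.3). Later SAEs judged at least possibly related remain reportable (Section 10.3.2). What is lost is scheduled collection of new non-serious events and later laboratory results.
- **Outcome-dependent removal is not shown.** A reader might suppose that taking a medicine for a symptom, or missing a visit through illness, would trigger removal. Section 6.10 permits medicines needed to treat an AE and exempts paracetamol and ibuprofen. Section 7.2, written for Period 2, has a missed visit skipped and does not call for withdrawal. Section 6.9 says "Any incidence of overdose should be recorded as a deviation", so a safety-relevant case could come under the rule, but it does not class overdose as major.
- **The synopsis does not contradict Section 7.1.2.** The synopsis sentence concerns stopping treatment, while Section 7.1.2 concerns leaving the study. The real mismatch is between the synopsis and Section 7.1.
- **Reduced-denominator confidence limits do not fit.** It is tempting to recompute an upper limit on the event rate with the withdrawn participant removed. The plan keeps that participant in the denominator and describes only descriptive summaries.
- **Deleting two list items would not be enough.** Section 7.1.2 also allows withdrawal for medical reasons at the investigator's discretion and for any reason at the sponsor's, with the same loss of follow-up.

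None of this answers the central gap: no text asks a dosed participant removed for a deviation to continue scheduled follow-up.

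**Conclusion.** The concern holds as a gap in the protocol that is worth closing. Followed as written, Section 7.1.2 shortens observation of the primary safety endpoint for a reason unrelated to participant safety, and in Period 1 it achieves nothing else after dosing. The loss can be most of the schedule, such as 70 of 84 days and 10 of 12 visits for an exit on Day 15, apart from the ET visit.

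That the primary endpoint is biased is not shown. The direction of any error in crude incidence is downward, but its size depends on how many are withdrawn, when, and when events occur, none of which the documents give. With one of 6 active participants truncated and equal risks assumed, expected incidence lies between 83% and 100% of its true value. The analyses are descriptive, so no error rate or power is affected. The difference between *major* and *important* is editorial, though it leaves the trigger undefined.

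**What to change.** In Section 7.1.2, state that a protocol deviation or noncompliance is not by itself a reason to end study follow-up of a dosed participant. State also that dosed participants removed on these or other investigator or sponsor discretionary grounds are asked to stay in scheduled safety follow-up to Day 85 (Period 1) or Day 113 (Period 2), unless consent is withdrawn or the study is terminated. Membership of the safety population needs no change.

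In the analysis plan, flag the deviation and exclude only the affected PK values.

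Reconcile Section 7.1 with the synopsis on what follows treatment discontinuation, and align the deviation term in Section 7.1.2 with the one defined in Section 10.5.2. Decisions on dosing stay under the existing rules.

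The cost is a wording amendment and some follow-up visits for participants who would otherwise have left, all of them already in the schedule. Sample size is unchanged.
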